- 5) If an SAE occurred, follow the instructions in [Section 10](#) for reporting it. Remind to notify the site in case of an SAE.
- 6) Complete the relevant CRFs for this visit.
- 7) Remind the parent / guardian / legally acceptable representative of the following visit.

Visit 03: Day 56+7 Post-Vaccination 1 Visit Procedures for Cohort 1 and 3

- 1) Review medical history, including past and ongoing medication since the last visit. Check for contraindications.
- 2) Perform a focused clinical examination including temperature, pulse, and respirations, EENT, respiratory, cardiac and lymphatic system.
- 3) Obtain a blood sample for serum antibodies to RSV (see [Section 7.1](#) for detailed instructions regarding the handling of blood samples).
- 4) Collect and review SAEs in the completed DC1 and DC2 / eDC with the participant's parent / guardian / legally authorized representative. Provide MA.
- 5) If an SAE had occurred, follow the instructions in [Section 10](#) for reporting it. Remind to notify the site in case of an SAE.
- 6) Complete the relevant CRFs for this visit.
- 7) Remind the parent / guardian / legally authorized representative of the following visit.

Visit 03: Day 56+7 Post-Vaccination 1 Visit Procedures for Cohorts 2 and 4

- 1) Obtain verbal medical history about the participant, including past and ongoing medication and immunizations.
- 2) Check for contraindications for receipt of second vaccination.
- 3) Prior to vaccination, conduct a focused clinical examination including temperature, pulse, and respirations, EENT, respiratory, cardiac and lymphatic system.
- 4) Perform COVID-19 POC diagnostic test.
- 5) Collect reportable concomitant medications / vaccinations.

- 6) Contact the IRT for dose number.
- 7) Obtain a blood sample for serum antibodies to RSV (see [Section 7.1](#) for detailed instructions regarding the handling of blood samples).
- 8) Administer the appropriate study product, follow the instructions provided for the intranasal administration of study vaccine using the [REDACTED] in the Study Operating Guideline.
- 9) Keep the participant under observation for 30 minutes and record any adverse reaction in the source document.
- 10) Collect and review solicited reactions and unsolicited AEs, including AESIs, MAAEs and SAEs in the completed DC1 and DC2 / eDC with the participant's parent / guardian / legally authorized representative.

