5.2.3 Screening Criteria

There are no screening criteria other than the inclusion and exclusion criteria. The Investigator must review the inclusion and exclusion criteria at enrollment (Visit 01).

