5.2.5 Exclusion Criteria

An individual fulfilling *any* of the following criteria is to be excluded from trial enrollment:

- 1) Participation at the time of study enrollment (or in the 6 weeks preceding the first trial vaccination) or planned participation during the present trial period in another clinical trial investigating a vaccine, drug, medical device, or medical procedure.
- 2) Receipt of any of the following vaccines prior to enrollment:
 - any influenza vaccine within 7 days prior, or
 - any inactivated vaccine within the 14 days prior, or
 - live-attenuated rotavirus vaccine within the 14 days prior, or
 - any live vaccine, other than rotavirus vaccine, within the 28 days prior, or
 - another investigational vaccine or investigational drug within 28 days prior.
- 3) Previous receipt of a licensed or investigational RSV vaccine or previous receipt or planned administration of any anti-RSV product (such as ribavirin or RSV immune globulin [IG] or RSV monoclonal antibody).
- 4) Receipt of immune globulins, blood or blood-derived products in the past 6 months prior to enrollment.
- 5) Known or suspected congenital or acquired immunodeficiency; or receipt of immunosuppressive therapy, such as anti-cancer chemotherapy or radiation therapy, within the preceding 6 months; or long-term systemic corticosteroid therapy (prednisone or equivalent for more than 2 consecutive weeks within the past 3 months).
- 6) Probable or confirmed case of Coronavirus Disease 2019 (COVID-19).
- 7) Known systemic hypersensitivity to any of the vaccine components, or history of a life-threatening reaction to the vaccine used in the trial or to a vaccine containing any of the same substances.^b

^a 6 through 18 months means from 6th month after birth to the day before the 19th month after birth.

^b The components of the study vaccine are listed in Section 6.1 and in the Investigator's Brochure.

- 8) Any chronic illness.
 - Chronic illness may include, but is not limited to, cardiac disorders, lung disease (including any history of reactive airway disease, receipt of bronchodilator therapy, or medically diagnosed wheezing), renal disorders, auto-immune disorders, diabetes, psychomotor diseases, and known congenital or genetic diseases
- 9) Any history of medically diagnosed wheezing.

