- 10) Any acute febrile, respiratory or gastrointestinal illness in the past 24 hours that according to investigator judgment is significant enough to interfere with successful inoculation on the day of vaccination. A prospective participant should not be included in the study until the condition has resolved or the febrile event has subsided.
- 11) Receipt of any of the following medications within 3 days prior to study enrollment:
 - systemic antibacterial, antiviral, antifungal, anti-parasitic, or antituberculous agents, whether for treatment or prophylaxis, or
 - intranasal medications, or
 - other prescription medication except as permitted concomitant medications (prescription or non-prescription) including nutritional supplements, medications for gastroesophageal reflux, eye drops, and topical medications, including (but not limited to) cutaneous (topical) steroids, topical antibiotics, and topical antifungal agents.
- 12) Receipt of salicylate (aspirin) or salicylate-containing products within the 28 days prior to enrollment.
- 13) Deprived of freedom in an emergency setting or hospitalized involuntarily.
- 14) Identified as a natural or adopted child of the Investigator or employee with direct involvement in the proposed study.
- 15) Any previous anaphylactic reaction.
- 16) Any previous vaccine-associated adverse reaction that was Grade 3 or above. Note: if grading is not possible, determine if the reaction was considered severe or life-threatening; if so, it is exclusionary.
- 17) Member of a household that contains, or will contain, an infant who is less than 6 months of age at the enrollment date (or in the 6 weeks preceding the first trial vaccination) through Day 28.
- 18) Member of a household that contains another child/other children who is/are, or is/are scheduled to be, enrolled in this study in the same year AND the date of enrollment will not be concurrent with the other participant(s) living in the household (i.e., all eligible children from the same household must be enrolled on the same date).
- 19) Member of a household that contains an immunocompromised individual, including, but not limited to:
 - a person who is HIV infected
 - a person who has received chemotherapy within the 12 months prior to enrollment
 - a person receiving immunosuppressant agents
 - a person living with a solid organ or bone marrow transplant.

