- 20) Attends a daycare facility and shares a daycare room with infants less than 6 months of age, and parent/ guardian / legally authorized representative is unable or unwilling to suspend daycare for 28 days following inoculation.
- 21) Scheduled administration of the following after planned inoculation:
 - any influenza vaccine within 7 days after, or
 - inactivated vaccine or live-attenuated rotavirus vaccine within the 14 days after, or
 - any live vaccine other than rotavirus in the 28 days after, or
 - another investigational vaccine or investigational drug in the 56 days after.
- 22) Born at less than 34 weeks gestation.
- 23) Born at less than 37 weeks gestation and less than 1 year of age at the time of enrollment.
- 24) Current suspected or documented developmental disorder, delay, or other developmental problem.
- 25) Any previous receipt of supplemental oxygen therapy in a home or hospital setting, except the temporary receipt of supplemental oxygen for transient tachypnea in newborn.

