5.2.7 Contraindications for Subsequent Vaccinations

5.2.7.1 Temporary Contraindications

Should a participant experience one of the conditions listed below at Day 0 (Cohorts 1, 2, 3 and 4) or Day 56 (Cohorts 2 and 4), the Investigator will postpone further vaccination until the condition is resolved. Postponement must still be within the timeframe for vaccination i.e., within 5 days of randomization for Day 0 (Cohorts 1, 2, 3 and 4) and within 7 days of Day 56 (Cohorts 2 and 4).

- 1) Any acute febrile illness (rectal temperature $\geq 38.0^{\circ}\text{C}$ [$\geq 100.4^{\circ}\text{F}$]), acute otitis media, upper and lower respiratory signs or symptoms (including but not limited to rhinorrhea, cough, and pharyngitis), or nasal congestion in the past 24 hours that according to investigator's judgment is significant enough to interfere with successful absorption of the study product.
- 2) Receipt of any of the following before any study vaccination or scheduled administration after any study vaccination:
 - any influenza vaccine within 7 days prior, or
 - any inactivated vaccine or live-attenuated rotavirus vaccine within the 14 days prior, or
 - any live vaccine, other than rotavirus vaccine, within the 28 days prior, or
 - another investigational vaccine or investigational drug within 28 days prior.

All eligible participants from the same household who are enrolled on the same date must receive the study product on the same date, and therefore if one child experiences illness as above, product administration should be deferred for both children.

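### Exclusion 17 stops at Day 28, so in the two-dose cohorts it does not bar a young infant who joins the household between Day 29 and 28 days after dose 2, and household contacts are not re-checked before that dose

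*Protocol*

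**What the plan says.** **Exclusion 17** (Protocol Section 5.2.5, repeated in the Synopsis) covers a household infant "less than 6 months of age at the enrollment date (or in the 6 weeks preceding the first trial vaccination) through Day 28". It names the first vaccination and closes on a study day.

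**Exclusion 19** bars a child living with an immunocompromised person. Its examples include "a person who has received chemotherapy within the 12 months prior to enrollment".

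**When the criteria are applied.** Section 5.2.3: "The Investigator must review the inclusion and exclusion criteria at enrollment (Visit 01"). The procedures tables mark the inclusion and exclusion criteria at Visit 01 and have no such row for the dose-2 period.

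**Before dose 2.** Section 5.1.4.1, Visit 03 for Cohorts 2 and 4, step 1: "Obtain verbal medical history about the participant, including past and ongoing medication and immunizations". Step 2: "Check for contraindications for receipt of second vaccination". The contraindications are in Section 5.2.7. The temporary ones are acute illness and recent vaccines or investigational products. The definitive ones are a significant allergic reaction, certain events related to the previous dose, and COVID-19. A postponed second dose must still be given "within 7 days of Day 56 (Cohorts 2 and 4").

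**What the protocol assumes about dose 2.** Section 9.1.1.1 gives it a separate Acute Phase, D56 to D84, and links the 28-day length to how long live-attenuated RSV is shed by seronegative children. A shedding swab is planned at D63.

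**The concern.** The end point of exclusion 17 fits a one-dose schedule. In Cohorts 1 and 3 it matches the single Acute Phase exactly. In Cohorts 2 and 4 it ends four weeks before the second administration.

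The protocol treats a very young infant or an immunocompromised person in the home as a reason not to give this live vaccine at Day 0. Followed as written, it would enroll a child whose household expects a birth on, say, Day 40, and would then give dose 2 with a newborn in the home. Likewise, a household member who starts chemotherapy on Day 45 triggers no rule that withholds dose 2.

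What is at stake is protection of contacts, not the validity of the analyses. The same safeguard should apply to both doses, or the protocol should say why it need not.

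**Working it through.** **Inputs.** Exclusion 17 window: closes at D28 (Section 5.2.5). Dose 2: D56, with a 7-day allowance (Sections 5.1.4.1 and 5.2.7.1). Follow-up after each dose: 28 days (Section 9.1.1.1). Group sizes: Cohort 2, 20 + 20; Cohort 4, 60 + 60 + 60 (Section 12.5).

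**1. Reproduce the protocol's own date.** End of the second Acute Phase = 56 + 28 = D84, as stated.

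**2. Latest case.** Latest dose 2 = 56 + 7 = D63. Its 28 days end on 63 + 28 = D91.

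**3. Overlap with exclusion 17.**

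| Dose | 28-day period | Calendar days | Days within D0–D28 |
|---|---|---|---|
| Dose 1, D0 | D0–D28 | 29 | 29 |
| Dose 2, D56 | D56–D84 | 29 | 0 |
| Dose 2, D63 | D63–D91 | 29 | 0 |

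The window closes 56 − 28 = 28 to 63 − 28 = 35 days before dose 2. The SAP (Section 5.2.3) accepts a second dose up to D66 for the per-protocol set. The overlap is still zero there, but that is an analysis rule and does not extend the dosing window.

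**4. Which infants are missed.** Zero overlap does not mean that any young infant may be present. An infant already in the home by D28 and still under 6 months at dose 2 was also under 6 months at D28, so exclusion 17 already applied. What remains is an infant under 6 months born into or joining the home:

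- from D29 to D84: 84 − 28 = 56 days; or
- from D29 to D91: 91 − 28 = 63 days, if dose 2 is given on D63.

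**5. Is there a later check?** The Visit 03 steps were read against Section 5.2.7. The history step concerns the participant. Neither contraindication list names a household infant or an immunocompromised household member. Exclusions 17 and 19 are therefore not re-applied before dose 2.

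**6. Who is affected.** Due a second administration: 40 + 180 = 220 of 300. Due a second administration of live vaccine: 20 + 60 + 60 = 140.

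The documents give no transmission rate and no rate at which households change between D0 and D56, so no expected number of exposed or infected contacts can be derived.

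**The case against.** **The risk after dose 2 is small.** Section 5.1.2 reports that second administrations of other RSV and PIV3 candidates were highly restricted, and Section 1.3.2 does not list spread to contacts. This stands and limits the weight of the point. It does not remove it. Section 5.1.2 also says the main effect of repeat dosing was to infect children who had not responded to the first dose. At one dose level in the earlier NIH study, 80% of recipients were infected (Section 1.1), so some children may first be infected at dose 2.

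**Practice may already cover it.** The Operating Guidelines are not among the documents, and a household check at Visit 03 could be there. The point is limited to the protocol text. Section 5.2.8 allows discretionary withdrawal from the study, but it names no household condition and does not address withholding a dose.

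**It comes late.** The version history runs to January 2023. The approximate calendar in Section 5.1.5 puts the last Cohort 4 contact at 30 April 2023. Five months earlier is about the end of November 2022, so on that calendar few or no second doses may remain. This affects how many children a change would still reach, not whether the rule fits a two-dose schedule.

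**Stronger readings that the documents do not support:**

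- *Exclusion 19 is worded for enrollment only.* Just the chemotherapy example is tied to enrollment; the stem and the example on immunosuppressant agents are in the present tense. The gap comes mainly from reviewing criteria only at Visit 01.
- *Exclusion 5 ("Known or suspected congenital or acquired immunodeficiency") is equally unguarded.* Visit 03 takes the child's history and medication, and Section 6.7.2 advises against immune-modifying drugs after study product. No listed contraindication stops dose 2 on this ground, but the investigator would be expected to learn of the condition. This is largely covered.
- *Exclusion 20 has the same fault.* It turns on a parent "unable or unwilling to suspend daycare for 28 days following inoculation", which names no dose number or study day and can be read as applying to each dose.

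**Conclusion.** The point holds in a limited form and is worth correcting. In Cohorts 2 and 4, exclusion 17 leaves a 56-day gap (63 days at the latest dose-2 date) for infants under 6 months who are born into or join the household after D28. Household immunocompromise arising after D0 is not re-checked before dose 2. The affected schedule covers 220 planned participants, 140 of them on live vaccine.

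Those counts are participants to whom the incomplete rule applies. A reader might take them as children dosed near a vulnerable contact, or as a measure of harm; the documents support neither. The conclusion assumes that Day 28 is a study day, which agrees with the D56 to D84 labels for dose 2, and that no re-check is set out in the Operating Guidelines. Estimates and analysis methods are not affected.

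**What to change.** 1. **Exclusion 17 (Section 5.2.5 and Synopsis).** Replace the Day 28 end point with *through 28 days after the last planned administration*. Cohorts 1 and 3 keep Day 28; Cohorts 2 and 4 move to about Day 84, up to Day 91 with the visit window.
2. **Section 5.2.7.2.** Add, for the second administration: *household contains, or is expected within 28 days to contain, an infant under 6 months, or contains an immunocompromised individual as listed in exclusion 19 (for chemotherapy, within 12 months of this administration)*. Dose 2 is withheld, and the section's existing provision for continued follow-up applies.
3. **Visit 03, step 1, Cohorts 2 and 4.** Add a question about household members, including any young infant present or expected in the next 28 days.

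**Cost.** The wording is short and the question falls at an existing visit, but the change is a protocol amendment needing IEC/IRB approval (Section 5.4). A few children may miss dose 2 and leave PPAS2 (Section 12.2.3); having had one administration, they stay in the FAS and SafAS. Households expecting a birth before about Day 84 to 91 could not enter a two-dose cohort. If second doses are already complete, the wording should be carried into later two-dose protocols.

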5.2.6 Medical History

Prior to enrollment, participants will be assessed for pre-existing conditions and illnesses, both past and ongoing. Any such conditions will be documented in the source document. Significant (clinically relevant) medical history (reported as diagnosis) including conditions/illnesses for which the participant is or has been followed by a physician or conditions/illnesses that could resume during the course of the study or lead to an SAE or to a repetitive outpatient care will be collected in the CRB. The significant medical history section of the CRB contains a core list of body systems and disorders that could be used to prompt comprehensive reporting, as well as space for the reporting of specific conditions and illnesses.

For each condition, the data collected will be limited to:

- Diagnosis (this is preferable to reporting signs and symptoms)
- Presence or absence of the condition at enrollment
- The reporting of signs and symptoms in lieu of a diagnosis is strongly discouraged.

Dates, medications, and body systems are not to be recorded, and the information collected will not be coded. The purpose of limited data is to assist in the later interpretation of safety data collected during the study.

5.2.7 Contraindications for Subsequent Vaccinations

5.2.7.1 Temporary Contraindications

Should a participant experience one of the conditions listed below at Day 0 (Cohorts 1, 2, 3 and 4) or Day 56 (Cohorts 2 and 4), the Investigator will postpone further vaccination until the condition is resolved. Postponement must still be within the timeframe for vaccination i.e., within 5 days of randomization for Day 0 (Cohorts 1, 2, 3 and 4) and within 7 days of Day 56 (Cohorts 2 and 4).

- 1) Any acute febrile illness (rectal temperature $\geq 38.0^{\circ}\text{C}$ [$\geq 100.4^{\circ}\text{F}$]), acute otitis media, upper and lower respiratory signs or symptoms (including but not limited to rhinorrhea, cough, and pharyngitis), or nasal congestion in the past 24 hours that according to investigator's judgment is significant enough to interfere with successful absorption of the study product.
- 2) Receipt of any of the following before any study vaccination or scheduled administration after any study vaccination:
 - any influenza vaccine within 7 days prior, or
 - any inactivated vaccine or live-attenuated rotavirus vaccine within the 14 days prior, or
 - any live vaccine, other than rotavirus vaccine, within the 28 days prior, or
 - another investigational vaccine or investigational drug within 28 days prior.

All eligible participants from the same household who are enrolled on the same date must receive the study product on the same date, and therefore if one child experiences illness as above, product administration should be deferred for both children.

5.2.7.2 Definitive Contraindications

Should a participant experience one of the conditions listed below, the Investigator will discontinue vaccination:

- 1) An anaphylactic or any other significant allergic reaction to the previous dose of vaccine.
- 2) Any AE greater than Grade 2, LRI of any grade or SAE assessed by the investigator as related to the previous dose of vaccine.
- 3) Diagnosis of COVID-19

Participants with a definitive contraindication will continue to be followed up for the study-defined safety and immunogenicity assessments, as applicable.

In the event of a local or national immunization program with a pandemic vaccine e.g. influenza, participants who receive pandemic vaccine at any time during the study will not be withdrawn from the study.

5.2.8 Conditions for Withdrawal

Parents / guardians / legally authorized representatives will be informed that they have the right to withdraw their child from the study at any time. Any participant who has received study product will be encouraged to remain in study follow-up for the duration of the study even if sample collection is refused.

A participant may be withdrawn from the study:

- At the request of the parent / guardian / legally authorized representative either verbally or in writing (i.e., withdrawal of consent/dropout).
- At the discretion of the Investigator or Sponsor due to safety concern of significant non-compliance with the protocol (based on the Investigator's judgment), without the parent's / guardian's / legally authorized representative's permission (i.e., non-compliant with the protocol/withdrawal).

The reason for a withdrawal or dropout should be clearly documented in the source documents and in the CRB.

The Investigator must determine whether voluntary withdrawal is due to safety concerns (in which case, the reason for discontinuation will be noted as “Adverse Event”) or for another reason.

Withdrawn participants will not be replaced.

For any participant who withdraws or is terminated from the study prior to scheduled completion of follow-up, study staff will document the reason for the withdrawal or termination in detail and will make every effort to complete the following final evaluations:

- 1) Obtain verbal medical history about the participant, including past and ongoing medication and immunizations.
- 2) Obtain a blood sample for serum antibodies to RSV if possible (see [Section 7.1](#) for detailed instructions regarding the handling of blood samples).
- 3) Obtain a nasal swab sample for quantification of vaccine virus shedding (if in the Acute Phase), other respiratory pathogens including a COVID-19 POC test on the discretion of the investigator.
- 4) Complete the relevant section of the CRF.

